A sample of 60 patients scheduled for HSCT in the treatment of MM will be recruited in the weeks to months prior to their hospitalization. Light therapy incorporating ambient systematic programmed light illumination (sPI) will be used in patient hospital rooms (during scheduled transplant) to control cancer-related fatigue (CRF). The FDA has certified that light therapy, like that used in this study, is a low-risk intervention. After initial assessment of CRF, depression, and sleep quality/quantity (baseline assessments), participants will be randomized to one of two treatment conditions: one with an active intervention, and one with a non-active comparison. During inpatient hospitalization, the active intervention will consist of the following regimen: high intensity bright-white light (1300 lux at the eyes) during morning hours (7AM to 10AM). The non-active comparison condition will receive half the intensity dim-white light of the active group (i.e., 90 lux at the eyes) during 7AM-10AM. These differences in lux intensity are not easily discernable. Following baseline, assessment of fatigue, sleep activity, depression, circadian rhythms, and quality of life will continue through the course of hospitalization (14-21 days of treatment, to determine immediate impact of sPI), then repeat at one month and threemonths post-discharge follow-ups (to determine lasting effects). Outcomes will be assessed through standardized scales (e.g., FACIT-Fatigue Scale) and objective measures (e.g., actigraphy, daysimeter for light monitoring, melatonin from urine collection, blood inflammatory markers, all explained below). This trial will: 1) be the first randomized clinical trial (RCT) to investigate the effects of sPI to prevent CRF and other biopsychosocial side effects of transplant; 2) focus on a distinct, relatively homogenous patient population (MM-HSCT patients) with high prevalence of CRF; and 3) explore possible circadian rhythm mediation via melatonin analysis and blood analysis. This investigation will have major public health relevance as it will determine if an inexpensive and low patient burden intervention (sPI) is able to control fatigue associated with medical illnesses and related problems.

1) Objectives

Specific Aims:

- **Aim 1: Determine if sPI results in significant prevention/reduction of the development of CRF, depression, sleep problems, circadian rhythm disruption and diminished quality of life compared to the comparison light condition.** Hypothesis 1a: HSCT patients exposed to sPI will report less CRF (measured by FACIT-Fatigue Scale), less depressive symptoms (measured by the CES-D/BDI-II), better sleep (measured subjectively by the Pittsburgh Sleep Quality Index, FACIT Fatigue Scale and objectively by actigraphy), and more synchronized activity circadian rhythms (measured by actigraphy) during the course of HSCT hospitalization compared to those patients in the low light comparison condition. Hypothesis 1b: HSCT patients receiving sPI will report positive effects on CRF, depression, sleep, and circadian rhythm disruption at one month and three-

	Protocol Name:	Systematic Programmed Illumination of Hospital Rooms to Prevent/Reduce Cancer-Related Fatigue during Autologous Stem Cell Transplantation for Multiple Myeloma
	Principal Investigator:	[name]; [contact]
	Primary Contact Name/Contact Info:	[name], [contact], [contact]
	Date Revised:	8/15/2019
	Study Number:	IF# 2517160 HS# 15-00777 GCO#: 15-2009

months after discharge and completion of the sPI intervention than those in the comparison condition.

- Aim 2: Explore whether the effects of sPI are mediated by changes in sleep, depressive symptoms, activity circadian rhythms, melatonin and/or inflammatory markers.** Hypothesis 2a: The effects of sPI on CRF are mediated by changes in sleep quality. Hypothesis 2b: The effects of sPI on CRF are mediated by changes in depressive symptoms. Hypothesis 2c: The effects of sPI on CRF are mediated by changes in activity circadian rhythms (measured via actigraphy and melatonin rhythmicity). Hypothesis 2d: the effects of sPI on CRF are mediated by changes in inflammatory markers. **Aim 3: Determine the feasibility and acceptability of sPI, actigraphy, urine collection and monitoring of light exposure.** Hypothesis 3a: Initiating the sPI environment in patient hospital rooms during inpatient procedures (HSCT and initial chemotherapy regimen to treat MM and related oncological diseases) will be tolerable among MM-HSCT patients and medical professionals. Hypothesis 3b: sPI will be feasible as an inpatient treatment method to prevent common circadian rhythm-based side effects observed with HSCT and subsequent chemotherapy. Hypothesis 3c: sPI implementation inpatient hospital rooms will maximize potential patient benefit while minimizing deviation from normal lighting fixture end-user experience for both HSCT patients and medical professionals. Hypothesis 3d: Actigraphy collection among HSCT patients will be acceptable as an assessment method before, during, and after HSCT. Hypothesis 3e: Urine collection among HSCT patients will be tolerable as an assessment method before and during hospital visit for HSCT. Hypothesis 3f: Monitoring of light exposure via Daysimeter data among HSCT patients will be acceptable as an assessment method before and during HSCT.

2) Background

Debilitating fatigue – a persistent sense of exhaustion frequently associated with a number of serious medical conditions, including cancer – can interfere with mood, activities of daily living, treatment compliance. Such fatigue is often associated with sleep problems, depression, quality of life, and agitation. Unfortunately, currently available interventions for CRF are, at best, only modestly effective. Pharmacological agents have been studied for CRF, but there is insufficient evidence to recommend their use. Non-pharmacological interventions have shown clinical benefit, but they can be labor-intensive, expensive, and cumbersome for patients. A promising alternative is light therapy.

Although CRF is well documented, it is difficult to characterize because it has a poorly delineated etiology. Circadian rhythm disruption (CRD) has been hypothesized to play an important role in the etiology of CRF by affecting multiple domains of psychosocial and physiological functioning. Circadian rhythms are generated and regulated by an internal biological clock located in the suprachiasmatic nucleus of the hypothalamus; they are biological cycles (e.g., changes in hormone secretion, body temperature, and sleep-wake activity cycles) that are slightly longer than 24 hours and are entrained to the 24-hour day by environmental time cues.

Bright light is one of the strongest synchronizers of circadian rhythms, which are maintained through entrainment by light exposure to the retina. Light therapy incorporating systematic exposure to bluish-

	Protocol Name:	Systematic Programmed Illumination of Hospital Rooms to Prevent/Reduce Cancer-Related Fatigue during Autologous Stem Cell Transplantation for Multiple Myeloma
	Principal Investigator:	[name]; [contact]
	Primary Contact Name/Contact Info:	[name], [contact], [contact]
	Date Revised:	8/15/2019
	Study Number:	IF# 2517160 HS# 15-00777 GCO#: 15-2009

white light is hypothesized to entrain circadian rhythms, which play a crucial role in the cellular and physiological functions of the brain and body. Indeed, disruption of these rhythms has been shown to affect sleep quantity and quality, depression, and fatigue among cancer patients. The proposed research will investigate the delivery of sPI via a novel delivery system to treat CRF, experienced by up to 80% of all cancer patients. Although CRF has been found to be related to CRD and it is known that bright light improves rhythms, the effect of sPI on CRF has not been investigated. Further, CRF has been found to be related to sleep disturbances, as well as to depression, yet the effect of sPI on these effects has not been explored.

Inflammatory response have been proposed to underlie CRF. There is an association between CRF among cancer patients and activation of pro-inflammatory signaling. For example, breast cancer survivors with persistent fatigue have elevated levels of markers associated with pro-inflammatory cytokine activity including Interleukin-1 receptor antagonist (IL-1ra), Interleukin-6 (IL-6), soluble tumor necrosis factor receptor type II (sTNF-RII), soluble intercellular adhesion molecule-1 (sICAM-1), and C-reactive protein (CRP). It has also been shown that chemotherapy leads to significant elevations in inflammation which is associated with increases in fatigue.

In the proposed preliminary feasibility research, sPI will deliver appropriately timed ambient, low-level, bluish-white light to patients during their hospital stay with floor lamps designed to deliver high circadian stimulation in the morning. We have selected cancer patients who are hospitalized for HSCT to treat MM because this population: (1) is relatively homogenous with a high prevalence of CRF, (2) can be studied prospectively across the course of HSCT, (3) permits careful monitoring of circadian rhythm entrainment through analysis of melatonin from urine obtained before, during and after HSCT, (4) regularly has blood drawn for clinical purposes and (5) allows assessment and control of confounding variables.

Preliminary research:

The proposed exploratory study builds on [name]’s, [name]’s, and [name]’s complementary areas of research. [name], [name] and colleagues’ ongoing investigation of BWL to treat CRF in cancer (including HSCT) survivors has formed the conceptual template for the proposed study and points to the potential importance of sPI in the prevention and treatment of CRF. In previous studies, they were able to retain 71% of participants, a retention rate that we also expect for the proposed protocol.

Both [name]’s and [name]’s work supports the proposed study in 6 ways: (1) It provides the conceptual rationale for light as an intervention for negative sequelae of cancer treatment; (2) It established the acceptability of light treatment by cancer patients; (3) It determined the overall feasibility of lighting interventions with a cancer population, indicating that patients were: a) able to implement the light intervention with minimal involvement by research staff, b) adherent to home-based treatment regimens, and c) able to successfully complete all study assessments; (4) It confirms a low-lux light treatment as an

	Protocol Name:	Systematic Programmed Illumination of Hospital Rooms to Prevent/Reduce Cancer-Related Fatigue during Autologous Stem Cell Transplantation for Multiple Myeloma
	Principal Investigator:	[name]; [contact]
	Primary Contact Name/Contact Info:	[name], [contact], [contact]
	Date Revised:	8/15/2019
	Study Number:	IF# 2517160 HS# 15-00777 GCO#: 15-2009

appropriate comparison condition; (5) It provides clear procedural guidelines; (6) It demonstrates the importance of examining sPI for the treatment of negative cancer sequelae as patients exposed to daily light entrainment showed clinical benefit.

[name] has shown that using an ambient light treatment can improve sleep and behavior in patients with Alzheimer’s disease and related dementia. Using knowledge of human circadian phototransduction, which is how the retina converts light signals into neural signals to the brain, [name] was able to provide most of the ambient light’s radiant power in a range that has the greatest effect on circadian rhythms. This allows us to reduce overall sPI light levels and make the emitted light more comfortable for patients, possibly increasing treatment compliance.

Recent work by [name], [name], and [name] revealed that breast cancer and HSCT patients were light-deprived. Compared to healthy adults in an illumination study who received 58 minutes of bright light per day, breast cancer patients during chemotherapy received only 35 minutes of bright light per day, and HSCT patients in our preliminary light exposure study for cancer-related fatigue only received 30 minutes of bright light per day. Their findings provide additional evidence that sPI may hold promise for patients who are light deprived.

3) Setting of the Human Research

Research procedures will be performed at the Icahn School of Medicine at Mount Sinai (MSH) and the Rensselaer’s Lighting Research Center (RLC).

The RPI LRC Biomarker Lab staff will be responsible for processing urine specimens, informing and assisting with all protocols performed at MSH, processing and analyzing data, and writing reports. The IRB at Rensselaer Polytechnic Institute is a full board review, and will assess and approve the proposed research protocol at one of their regularly scheduled meetings.

Mount Sinai’s Human Immune Monitoring Core Shared Resource Facility staff will be responsible for storing and processing blood samples.

4) Resources Available to Conduct the Human Research

[figure not shown]
Cancer survivors who will receive autologous HSCT for treatment of MM will be recruited from Mount Sinai. All patients will be randomly assigned to either the active or comparison condition. We expect to recruit 60 patients over the study course. It is estimated that over 100 MM patients are seen at MSH annually to receive their first HSCT.

Research study personnel are very experienced with these types of studies. Research coordinators are highly qualified to assume these roles of screening and evaluating subjects, obtaining informed consent, analyzing and interpreting complex clinical research data, ensuring accurate and complete compilation of subject data, and liaising with the IRB of Protection of Human Subjects issues.

	Protocol Name:	Systematic Programmed Illumination of Hospital Rooms to Prevent/Reduce Cancer-Related Fatigue during Autologous Stem Cell Transplantation for Multiple Myeloma
	Principal Investigator:	[name]; [contact]
	Primary Contact Name/Contact Info:	[name], [contact], [contact]
	Date Revised:	8/15/2019
	Study Number:	IF# 2517160 HS# 15-00777 GCO#: 15-2009

To ensure that all study personnel are adequately informed about the protocol, all investigators, consultants and research coordinators will be required to read the protocol and to review the measures and equipment. We will also develop a recruitment script that the research coordinator will practice before reaching out to potential participants.

5) Study Design

a) Recruitment Methods

Potential participants will be identified by [name], and staff from the group of patients who will be undergoing their first autologous HCST and meet the additional inclusion criteria in EPIC. Prior to

	Protocol Name:	Systematic Programmed Illumination of Hospital Rooms to Prevent/Reduce Cancer-Related Fatigue during Autologous Stem Cell Transplantation for Multiple Myeloma
	Principal Investigator:	[name]; [contact]
	Primary Contact Name/Contact Info:	[name], [contact], [contact]
	Date Revised:	8/15/2019
	Study Number:	IF# 2517160 HS# 15-00777 GCO#: 15-2009

autologous HCST, the treating physician will discuss the study to their patient and inform them that they may be approached by a RA for participation. Additionally, a letter will be given to the patient, signed by the Director of the Multiple Myeloma program, introducing the study, team members, and to seek interest in participation. The following week, the RA will approach patients at their medical appointment at MSH in the months leading up to transplantation, unless the patient has expressed an unwillingness to participate. Physicians will inform RAs of those patients who have asked to not be approached for recruitment. The RC will then describe the study to determine their interest in participating, answer questions, and obtain Consent/HIPAA approval. A brief screening will subsequently be given to assess patient eligibility based on inclusion/exclusion criteria as listed in b) below. If there are any incidental findings during the screening and consent process, the subjects will be put in contact with a supervising licensed psychologist. The research team will look at each subject's CES-D scores at all timepoints to determine if they are at risk for severe depression. The protocol states that if a CES-D score is above 16, then the supervising psychologist will call the patient to determine if they need to be referred to get professional help regarding potential clinical depression. The BDI-II also can be used as a screener for depression. If a subject endorses suicidal ideation (by answering 2 or 3 for question 9, or scores in the severely depressed range between 29-63), then the supervising psychologist will also call the patient.

b) Inclusion and Exclusion Criteria

Our eligibility criteria includes:

Patients:

- Who will undergo their first autologous HSCT procedure as treatment for multiple myeloma
- AND:
- Who are currently 21 years of age or older
- English language proficient
- Able to provide informed consent

Exclusion criteria will be:

- Under age 21
- Previous HSCT procedure (autologous or allogeneic)Pregnancy
- Eye Diseases which limit the ability of light to be processed (e.g., untreated cataracts, severe glaucoma, macular degeneration, blindness, pupil dilation problems or retina damage)
- Secondary cancer diagnosis within the last 5 years
- Severe sleep disorders (e.g., Narcolepsy)
- History of bipolar disorder or manic episodes (which is a contra-indication for light treatment)
- Severe psychological impairment (e.g., hospitalization for depressive episode in the past 12 months)
- Previous use of light therapy to alleviate fatigue or depressive symptoms

c) Number of Subjects

 Mount Sinai	Protocol Name:	Systematic Programmed Illumination of Hospital Rooms to Prevent/Reduce Cancer-Related Fatigue during Autologous Stem Cell Transplantation for Multiple Myeloma
	Principal Investigator:	[name]; [contact]
	Primary Contact Name/Contact Info:	[name], [contact], [contact]
	Date Revised:	8/15/2019
	Study Number:	IF# 2517160 HS# 15-00777 GCO#: 15-2009

For this feasibility study, we will recruit 60 participants drawn from the pool of upcoming HSCT admissions to treat MM at the MSH bone marrow transplant (BMT) clinic. Our previous research has demonstrated that at least 40% of this group either suffers from or will develop clinically significant fatigue related to cancer or its treatment.

d) Study Timelines

Total participation in this study is 16-18 weeks, and may vary by hospital admission, length of hospital stay, and expediency of returning study related materials.

Endpoints

The primary endpoints in the proposed study are: 1) Fatigue as measured by a simple Graphic Rating Scale, Multidimensional Fatigue FACIT Fatigue Scale, and The Pittsburgh Sleep Quality Index; 3) Depression as measured by the CES-D; 4) Quality of Life measured by the SF-36 scale; 5) Sleep/wake activity measured using an actigraph; and 7) Biological variables melatonin and inflammatory markers (i.e., IL-1ra, IL-6, MCP-1/CCL2, MIP-1a/CCL3, sTNFr1, sIL-6R, CRP) as obtained via urine and blood analysis.

The secondary endpoints include: 1) the amount of light received by the patient as measured by the Daysimeter; 2) treatment satisfaction using the FACIT-TS-G scale, and 3) Psychological moderators (e.g., emotions, symptom burden) that may affect for whom the treatment is effective.

With regard to safety endpoints, there are no known major risks associated with the use of bright white light in the treatment of either fatigue or depression. However, we will monitor those who decide to cease treatment because they find the treatment approach unacceptable along with their concerns regarding treatment.

e) Procedures Involved in the Human Research

Approach: We will explore the acceptability, feasibility and potential efficacy of sPI exposure to prevent CRF in patients undergoing initial autologous HSCT, as provided during their inpatient hospital stay for approximately two weeks following transplant. We will also determine the feasibility of investigating biological markers (i.e. melatonin, inflammatory markers) as mediators of the clinical impact on CRF. Urine samples will be collected at two timepoints to assess melatonin rhythmicity. Blood samples will be collected at four timepoints to assess the inflammatory response in relationship to the light treatment.

The proposed approach will be informed by procedures [name] developed for her recent research on sLE treatment in Alzheimer's patients. Additionally, we will be building on our previously established protocols to inform our ability to research sPI treatment. The two teams of investigators will work closely, carrying out weekly conference calls and quarterly face-to-face meetings alternating between MSH and Rensselaer Polytechnic Institute (RPI). The MSH team will recruit study participants and oversee use of the light fixtures, monitoring equipment, assessment scales, and facilitate with [name]'s laboratory regarding proper storage and analysis of urine samples. MSH will also collaborate with the Mount Sinai's Human

	Protocol Name:	Systematic Programmed Illumination of Hospital Rooms to Prevent/Reduce Cancer-Related Fatigue during Autologous Stem Cell Transplantation for Multiple Myeloma
	Principal Investigator:	[name]; [contact]
	Primary Contact Name/Contact Info:	[name], [contact], [contact]
	Date Revised:	8/15/2019
	Study Number:	IF# 2517160 HS# 15-00777 GCO#: 15-2009

Immune Monitoring Core Shared Resource Facility at Mount Sinai to process and analyze blood samples to assess and track inflammatory markers.

Actigraphs will be used to monitor bio-behavioral indicators of circadian rhythms. The Actigraph is attached to the non-dominant wrist and measures movement and activity. The Daysimeter is worn around the neck and measures light exposure.

Acuity Lighting Brands will be providing the lighting fixtures in patient rooms at no cost. The fixtures will control all emitted wavelengths and provide both treatment and comparison conditions from the same fixture, as controlled by the investigators.

Methods: MM patients who will receive an autologous HSCT as part of their treatment plan will be recruited from MSH, and will be randomly assigned to either the BWL or the DWL conditions. Participants in both treatment arms will complete baseline 1 assessment at the time they are recruited. If Baseline 1 is completed more than two months before transplant participants will complete baseline 2 approximately one month before their transplant. After the baseline(s) assessment participants will be assessed: (A) during the inpatient hospital stay at day of transplant, day + 2, day + 7; (B) engraftment day 3 (most likely during week 2-3); (C) one month after hospital discharge; and (D) three months after hospital discharge. Outcome measures include standardized questionnaire measures of CRF, depression, sleep quality, and quality of life, as well as analysis of urinary melatonin and blood inflammatory marker levels at both outpatient and inpatient timepoints to monitor the biological processes believed to be influenced by sPI. This assessment schedule will allow us to evaluate the immediate and post-treatment benefits of the sPI treatment.

The proposed statistical analyses examine a number of related questions. The first consists of a comparison of the impact of the sPI exposure intervention to a comparison condition on CRF, depression, sleep quality, circadian rhythmicity, and quality of life using both the self-report and objective outcome measures (i.e. actigraphy data) in MM patients undergoing autologous HSCT. The second will examine the possible mediating role of depression, sleep quality, circadian activity rhythms, and fatigue on the effects of sPI. Lastly, the third will assess the feasibility and acceptability of an sPI intervention, actigraphy, urine melatonin analysis, and light exposure monitoring during HSCT. We will also look at possible co-moderators that may influence for whom the treatment works as defined by the list of additional measures we have included. In addition, we will explore whether the light treatment improves fatigue and depression through biological mediators analyzed in blood, i.e. inflammatory markers.

Please see the Data Safety and Monitoring Plan in section 5h for procedures taken to lessen the probability or magnitude of risks.

Data about subjects will be collected from medical charts, urine samples, blood samples, questionnaires that the participants will fill out, and output from the equipment (i.e., Actigraph and Daysimeter data).

 Mount Sinai	Protocol Name:	Systematic Programmed Illumination of Hospital Rooms to Prevent/Reduce Cancer-Related Fatigue during Autologous Stem Cell Transplantation for Multiple Myeloma
	Principal Investigator:	[name]; [contact]
	Primary Contact Name/Contact Info:	[name], [contact], [contact]
	Date Revised:	8/15/2019
	Study Number:	IF# 2517160 HS# 15-00777 GCO#: 15-2009

If there are any adverse events during the screening and consent process, the study participants will have the option to be put in contact with the a licensed clinical psychologist. The suicidality protocol will be in place throughout the entire study. It will be in the judgment of the consenting professional and/or as per medical record to determine if a patient may have severe psychopathology or cognitive impairment likely to interfere with the participation or completion of the protocol or ability to provide meaningful information. In this case, professional will decide not to include potential participant in the study.

The following questionnaires will be completed during the study:

Background Measures:

- Background Information Questionnaire – Socio-demographic data regarding gender, age, ethnicity, religion, income, marital status, and employment status will be gathered during the screening assessment and any changes in information will be gathered at the follow-up assessments. We will assess co-morbid medical conditions and current prescription sleep-related and non-sleep-related medications.
- Chronotype (MEQ) – We will collect data on baseline circadian predispositions using the Morningness-Eveningness Questionnaire, a 19-item self-rated survey designed to measure whether a person’s peak alertness is in the morning or the evening. Takes approximately 2 minutes to complete.

Credibility Measures:

- Credibility/Expectancy Questionnaire – This questionnaire will ask whether the patient feels the light box is a useful and/or effective treatment for CRF.

Sleep and Fatigue Measures:

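### The stated light levels for the two arms contradict each other: 1300 lux active, a comparison at half of that, and a comparison of 90 lux cannot all hold

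*Combined protocol and SAP*

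**What the plan says.** The summary that precedes 1) Objectives specifies both arms in consecutive sentences. The active arm receives "high intensity bright-white light (1300 lux at the eyes) during morning hours (7AM to 10AM"). The comparison arm receives "half the intensity dim-white light of the active group (i.e., 90 lux at the eyes") between the same clock times. The summary then adds: "These differences in lux intensity are not easily discernable".

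Elsewhere the light is described only in words:

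- 1) Objectives, Aim 1, frames the test as sPI patients "compared to those patients in the low light comparison condition".
- 2) Background says "sPI will deliver appropriately timed ambient, low-level, bluish-white light to patients during their hospital stay".
- Under Preliminary research, the earlier work is said to support a low-lux comparison ("It confirms a low-lux light treatment as an" appropriate comparator), and of the spectral design the text says "This allows us to reduce overall sPI light levels".
- 5) e) Procedures labels the arms BWL and DWL, both delivered by one investigator-controlled fixture.
- 6) Risks to Subjects says only that study levels are below the 10,000 lux of typical light boxes.

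**The concern.** The comparison level is specified twice in one phrase, once as a fraction of the active level and once in lux, and the two are presented as the same thing. They are not the same if the active level is 1300 lux. The reader cannot tell whether the slip is in the active level, the comparison level or the fraction.

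The light level at the eye is the only difference between the arms that the summary states. Aim 1 tests that difference, and the Power text in 5) g) wants the resulting effect sizes to inform the sample size of a larger study. An effect estimate is hard to carry forward if the contrast that produced it is not settled.

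The statement that the levels are hard to tell apart also depends on the size of the contrast, because a 2:1 difference and a 14.4:1 difference are different claims. This bears on fatigue, which 5) g) Data Analysis names as the primary outcome and which is measured by self-report scales.

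**Working it through.** **Inputs**, all from the summary before 1) Objectives:

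- A: active level = 1300 lux at the eyes, 7AM to 10AM.
- C: comparison level = 90 lux at the eyes, same hours.
- F: comparison/active = 0.5.

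**Attempt to reproduce the plan's figure.** F × A = 0.5 × 1300 = 650 lux. The plan states 90, so the figure is not reproduced.

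**Inverse.** C / F = 90 / 0.5 = 180 lux. The plan states 1300, so this is not reproduced either.

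**Ratio of the two stated levels.** 90 / 1300 = 6.9%; 1300 / 90 = 14.4.

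**Could half refer to some other scale of intensity?** The ratio of comparison to active is:

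- log10 scale: log10(90) / log10(1300) = 0.63
- square-root scale: √(90/1300) = 0.26
- cube-root scale: (90/1300)^(1/3) = 0.41

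None of these is one half. In any case, the sentence that follows speaks of lux.

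**Could the place or time of measurement differ?** No. Both levels are given at the eyes and for the same three hours.

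**What each pair of statements implies:**

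| Statements kept | Active (lux) | Comparison (lux) | Ratio | Difference (lux) | Lux-hours per day over 3 h |
|---|---|---|---|---|---|
| A and C | 1300 | 90 | 14.4:1 | 1300 − 90 = 1210 | 3900 vs 270 |
| A and F | 1300 | 650 | 2:1 | 1300 − 650 = 650 | 3900 vs 1950 |
| C and F | 180 | 90 | 2:1 | 180 − 90 = 90 | 540 vs 270 |

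The difference between arms therefore runs from 90 to 1210 lux (1210 / 90 = 13.4-fold). That range only illustrates how far apart the readings are. It enters no analysis.

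**Does the rest of the text choose between the readings?** The bound in 6) Risks to Subjects does not: 1300 / 10,000 = 13% and 180 / 10,000 = 1.8%, so both active levels lie below it. The verbal descriptions carry no number and do not settle the matter.

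**The case against.** The strongest reply is that the summary gives an explicit lux figure for each arm, so the protocol is not silent on levels and the fraction may just be loose wording. That may be so, but the document does not say it. The fraction is tied directly to 90 lux, and 180 versus 90 would satisfy that phrase exactly. Choosing a reading would be a guess.

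Three other points stand, and they limit the finding:

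- The descriptive wording elsewhere is not a second error. Light well below a 10,000 lux box can be called low-level and still be high intensity relative to the other arm. BWL and DWL match the bright-white and dim-white labels of the summary.
- This is a feasibility study, and no stated power, sample size or analysis uses lux.
- The defect shown is in the specification. The fixtures may be set correctly and consistently.

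One might add that the Daysimeter, a secondary endpoint under Endpoints in 5) d), will record the light received. It helps only in part. Under 5) e) it is worn around the neck, so it approximates light at the eye. The wear period in 5) f) is a 72-hour span at baseline and then a period in hospital before discharge, so inpatient coverage may be incomplete. It also measures received light, not the intended setting.

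**Conclusion.** The contradiction is real and follows from the plan's own figures. The three statements cannot all be true, and the planned contrast is 1210, 650 or 90 lux according to which one is wrong. It needs correcting because it concerns the definition of the randomized comparison, and no operational section resolves it. The conclusion assumes that the levels are in lux at the eye in the same window, as written. It is limited to the text available for review; material removed from the front of the document could not be checked. It takes no position on which statement is right.

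**What to change.** The sponsor should check the actual fixture settings for both arms, reconcile the active level, the comparison level and the stated fraction against them, and state one level at the eye for each arm. Once that is done, the sponsor should reread the sentence on discernibility and either confirm that it applies to the reconciled contrast or reword it. That is a follow-on check, not a separate error.

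Optionally, Daysimeter exposure and Credibility/Expectancy scores could be reported by arm. The limits of the Daysimeter are noted above. The questionnaire has no stated timepoint and measures credibility, not a guess of assignment. Section 5) h) already plans a three-monthly review of expectancy and blinding as part of trial monitoring.

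The cost is a wording change and a settings check. The optional summaries use data the study already collects.
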